6.6 Health-related Quality-of-Life or Health Economics Analyses Set(s)

Not Applicable

6.7 Pharmacokinetic/Pharmacodynamic Analyses Set(s)

The PK/PDn Analysis Set will include a subset of up to 20 evaluable subjects in Safety Analysis Set, who have consented to participate in the optional PK/PDn substudy. Evaluable subjects are defined as those subjects receiving at least 1 dose of carfilzomib and 1 post-dose PK and/or PDn sample collected, as defined by the Schedule of Assessments. These subjects will be evaluated for pharmacokinetics and pharmacodynamics unless significant protocol deviations affect data analysis or if key dosing, dosing interruption, or sampling information is missing.

6.8 Interim Analyses Set(s)

There are no formal interim analyses planned for this study.

6.9 Study-specific Analysis Sets

Not Applicable

7. Planned Analyses

7.1 Primary Analysis

The primary analysis will be triggered **12 months after the last subject enrollment**. The primary analysis will be based on a clean database lock.

7.2 Sustained MRD Analysis

A sustained **durable** MRD analysis is planned after all subjects have had the opportunity to complete their 24 months landmark MRD assessments. The analysis will be based on a clean database lock.

7.3 Data Review Team Early Stopping Guidelines

A data review team (DRT) is a group internal to Amgen, but external to the carfilzomib product team(s). The DRT is composed of members that are external to the study team and include a clinician, a safety physician, and a biostatistician. The DRT will review accumulating safety data from the ongoing clinical trial to ensure no avoidable that there is no increased risk for harm to subjects. Membership, procedures, and meeting timing will be described in detail in the study DRT charter.

7.4 Final Analysis

The final analysis is planned after all subjects have had the opportunity to complete their end of study visit. The analysis will be based on a clean database lock.

8. Data Screening and Acceptance

8.1 General Principles

The objective of the data screening is to assess the quantity, quality, and statistical characteristics of the data relative to the requirements of the planned analyses.

8.2 Data Handling and Electronic Transfer of Data

The Amgen Global Study Operations-Data Management (GSO-DM) department will provide all data to be used in the planned analyses. This study will use the RAVE database.

8.3 Handling of Missing and Incomplete Data

No imputation for missing data **of outcomes** will be performed; Sensitivity analyses **might be needed** to evaluate the robustness of the primary analysis. The handling of Incomplete dates for the start and **stop** of adverse event, concomitant medications, **new antimyeloma therapy, death, prior multiple myeloma therapy, and relapse/progression to prior multiple myeloma therapy** are described in [Appendix A](#)

8.4 Detection of Bias

If applicable the methods to detect bias are described in the analyses of particular endpoints.

8.5 Outliers

Pharmacokinetic (PK) plasma concentration data will be evaluated for outliers by visual inspection, and decisions to re-assay individual samples will be made in accordance with standard pharmacokinetic evaluation practice.

8.6 Distributional Characteristics

Not Applicable

8.7 Validation of Statistical Analyses

Programs will be developed and maintained, and output will be verified in accordance with current risk-based quality control procedures.

Tables, figures, and listings will be produced with validated standard macro programs where standard macros can produce the specified outputs.

The production environment for statistical analyses consists of Amgen-supported versions of statistical analysis software; for example, the SAS System version 9.4 or later.

9. Statistical Methods of Analysis

9.1 General Considerations

The analyses of efficacy and safety will be based on the safety analysis set. In principle, continuous variables will be summarized by the non-missing sample size (n), mean, standard deviation, median, minimum, and maximum.

Categorical variables will be summarized by the n and percentage in each category.

Time to event endpoints will be summarized with Kaplan-Meier (KM) curves, KM proportions at select time points, KM quartiles (when estimable), the number of subjects with events, the number of subjects censored, and censoring reasons.

Duration of follow-up for time to event endpoints will be estimated using the reverse Kaplan Meier method (Schemper and Smith, 1996). Point estimates for efficacy endpoints will be accompanied by 2-sided 90% and 95% CIs including estimates of KM quartiles (Klein and Moeschberger, 1997), KM proportions (Kalbfleisch and Prentice, 1980), and binomial proportions (Clopper and Pearson, 1934).

The evaluation of whether the key secondary objective was met will follow a fixed-sequence approach using the 90% exact confidence interval: the key secondary objective is met only after the primary objective is met.

9.2 Subject Accountability

The following subject disposition information will be summarized descriptively:

- Number of screened subjects
- Number of subjects screened but not **enrolled** (screen failures)
- **Number of subjects enrolled but not dosed**
- Number of treated subjects (Safety population)
- Number (%) of subjects who discontinued treatment and the primary reason for discontinuation. The percentage is calculated with respect to Safety population.

- Number (%) of subjects who discontinued study and the primary reason for discontinuation. The percentage is calculated with respect to safety population.
- Number (%) of subjects who entered long-term follow-up before disease progression. The percentage is calculated with respect to safety population.
- Number (%) of subjects who entered long-term follow-up for survival. The percentage is calculated with respect to safety population.
- **Number (%) of subjects who discontinued each study treatment (carfilzomib, dexamethasone, pomalidomide) or end of study due to COVID-19 control measures**

9.3 Important Protocol Deviations

Important Protocol Deviations (IPDs) categories are defined by the study team before the first subject's initial visit and updated during the IPD reviews throughout the study prior to database lock. These definitions of IPD categories, subcategory codes, and descriptions will be used during the course of the study. Eligibility deviations are defined in the protocol. **The following information of IPD and protocol deviations will be summarized, where applicable, with respect to the following:**

- **Number (%) of subjects with IPDs and total number of IPDs will be summarized by category and sub-category by treatment arm in Safety Analysis Set**
- **Number (%) of subjects with IPDs related to COVID-19 control measures will be summarized by treatment arm in Safety Analysis Set**
- **Number (%) of subjects with IPDs related to COVID-19 control measures by protocol deviation category (940 series, 950 series and 960 series of protocol deviations codes) and by treatment arm in Safety Analysis Set**
- **Subject listing of IPD in Safety Analysis Set, including IPDs related to COVID-19 control measures with the descriptions.**
- **Subject listing of IPDs related to COVID-19 control measures based on protocol deviations category (940 series, 950 series and 960 series of protocol deviations codes) in Safety Analysis Set**

In addition to the summary of IPD, subject listing of inclusion/exclusion deviations will also be generated.

9.4 Demographic and Baseline Characteristics

The following demographic, baseline characteristics and baseline disease characteristics will be summarized for the Safety Analysis Set. These includes but not limited to the following,

- **Baseline demographic and Baseline characteristics**

- Age (years) (as continuous variable; as categorical variable: 18 to < 65, 65 to < 75, 75 to < 85, ≥ 85 years; **<65, ≥65; 18-<65, 65-<75, ≥75**)
- Sex (Male, Female)
- Ethnicity (Hispanic or Latino, Not Hispanic or Latino)
- Race (**If multiple races have been reported for a subject, the subject will be categorized as multiple race**)
- Region (**Europe, Non-Europe**)
- Weight (kg)
- Height (cm)
- Body mass index
- Body Surface Area (m²) (as continuous variable; as categorical variable: ≤ 2.2, > 2.2 m²)
- ECOG performance status (0, 1, 2)
- Hemoglobin (g/L) (as continuous variable; as categorical variable: < 105, ≥ 105 g/L)
- Absolute Neutrophil count (10⁹/L) (as continuous variable; as categorical variable: < 1.5, ≥ 1.5 * 10⁹/L)
- Platelet count (10⁹/L) (as continuous variable; as categorical variable: < 150, ≥ 150 * 10⁹/L)
- Corrected calcium (mg/dL) (as continuous variable; as categorical variable: ≤ 11.5, > 11.5 mg/dL)
- Creatinine clearance (CrCl, mL/min) (as continuous variable; as categorical variable: < 30, 30 - < 50, 50 - < 80, ≥ 80 mL/min)

Measured or calculated accordingly to the Cockcroft-Gault formula:

$$CrCl (mL/min) = \frac{(140 - Age(years)) \times Weight(kg)}{72 \times Serum Creatinine(mg/dL)} \times (0.85 \text{ female})$$

- Baseline LVEF (%)
- Hypertension history (yes, no)
- Cardiopulmonary history (yes **<by diagnosis category>**, no)

- **Baseline Disease characteristics**

- ISS stage at baseline (stage I, II, III)
- Revised ISS stage at baseline (stage I, II, III)

- **Prior lenalidomide treatment (yes, no)**
- **Refractory to prior lenalidomide treatment (yes, no)**
- **Prior PI treatment (yes, no)**
- **Prior anti-CD38 exposure (yes, no)**
- **Refractory to prior anti-CD38 treatment (yes, no)**
- **Prior bortezomib treatment (yes, no)**
- **Refractory to prior bortezomib treatment (yes, no)**
- Time (month) since initial diagnosis
- Type of measurable disease (both SPEP and UPEP, SPEP only, UPEP only, Free light chain and abnormal Kappa/Lambda ratio (SFLC) only)
- Plasma cell involvement in bone marrow (%)
- MM subtype and immunoglobulin heavy chain and Light chain types (IgG, IgA, IgD, IgE, IgM, None; Kappa, Lambda, Not detectable within each subtype)
- Baseline beta2 microglobulin (mg/L) (as continuous variable; as categorical variable: < 3.5, 3.5 - < 5.5, ≥ 5.5 mg/L)
- Presence of plasmacytoma (yes, no)
- Prior Transplant (yes (Autologous, Allogeneic), no)
- **Prior tobacco use (yes, no)**
- Number of prior lines of therapy
- **Cytogenetic risk measured by FISH (high risk (t(4;14), t(14;16), deletion 17p), standard risk, missing)**
- Refractory to the last prior line of therapy
- **Albumin (g/dL) (as continuous variables; as categorical variable: <3.5, >=3.5)**
- Timing of refractoriness to Lenalidomide (during maintenance: yes vs no)
- **Time since last relapse (months)**

9.5 Efficacy Analyses

The primary analyses will be based on the safety analysis set, **while sensitivity analyses will use different population analysis set listed in [Table 9-1](#).**

Table 9-1. Primary Efficacy Endpoint Summary Table

Endpoint	Primary Summary and Analysis Method (Specify Analysis Set if FAS is Not Used)	Sensitivity Analysis
Overall Response Rate (ORR)	Safety Analysis Set: 
 • Based on Independent Review Committee 	Investigator Assessment 
 • Same as per primary analysis method

Endpoint	Primary Summary and Analysis Method (Specify Analysis Set if FAS is Not Used)	Sensitivity Analysis
	
 rate will be calculated along with the associated 90% and 95% exact binomial CIs that will be estimated using the Clopper-Pearson method. 	
based on Investigator assessment
 
Internal computational assessment:
 
 Same as per primary analysis method based on ORCA assessment. 
Per protocol population
 
 Same as per primary analysis method based on per protocol population 
Modified safety population
 
 Same as per primary analysis method based on modified safety population.

Table 9-2. Secondary Efficacy Endpoint Summary Table

Endpoint	Primary Summary and Analysis Method (Specify Analysis Set if FAS is Not Used)	Sensitivity Analysis

MRD[-]CR at a sensitivity of 10⁻⁵ using next generation sequencing (NGS)-based method in the bone marrow at 12 months ± 4 weeks from start of treatment.
	
Safety Analysis Set:
 
 Based on Independent Review Committee The rate will be calculated along with the associated 90% and 95% exact binomial CIs that will be estimated using the Clopper-Pearson method. 	
Investigator Assessment
 
 Same as per primary analysis method based on Investigator assessment 
Internal computational assessment:
 
 Same as per primary analysis method based on ORCA assessment. 
MRD-evaluable analysis Set:
 
 Same method as for primary analysis will be performed. 
Per protocol population
 
 Same as per primary analysis method based on per protocol population

Endpoint	Primary Summary and Analysis Method (Specify Analysis Set if FAS is Not Used)	Sensitivity Analysis
		
Modified safety population
 
 • Same as per primary analysis method based on modified safety population.

MRD response at a sensitivity of 10^{-5} using next generation sequencing (NGS)-based method in the bone marrow at any time during therapy
	
Safety Analysis Set:
 
 • Based on Independent Review Committee • The rate will be calculated along with the associated 90% and 95% exact binomial CIs that will be estimated using the Clopper-Pearson method. 	
Investigator Assessment
 
 • Same as per primary analysis method based on Investigator assessment 
Internal computational assessment:
 
 • Same as per primary analysis method based on ORCA assessment. 
MRD-evaluable analysis Set:
 
 • Same method as for primary analysis will be performed.

Sustained MRD[-]CR
	
Safety Analysis Set:
 
 • Based on Independent Review Committee • The rate will be calculated along with the associated 90% and 95% exact binomial CIs that will be estimated using the Clopper-Pearson method. 	
Investigator Assessment
 
 • Same as per primary analysis method based on Investigator assessment 
Internal computational assessment:
 
 • Same as per primary analysis method based on ORCA assessment. 
MRD-evaluable analysis Set:
 
 • Same method as for primary analysis will be performed.

Sustained MRD[-]CR response at 24 months \pm 4 weeks
	
Safety Analysis Set:
 
 • Based on Independent Review Committee • The rate will be calculated along with the associated 90% and 95% exact binomial CIs that will be estimated using the Clopper-Pearson method. 	
Investigator Assessment
 
 • Same as per primary analysis method based on Investigator assessment 
Internal computational assessment:
 
 • Same as per primary analysis method

Endpoint	Primary Summary and Analysis Method (Specify Analysis Set if FAS is Not Used)	Sensitivity Analysis
		based on ORCA assessment. MRD-evaluable analysis Set: 
 • Same method as for primary analysis will be performed.
Duration of Response	Safety Analysis Set: 
 • Based on Independent Review Committee • The distribution of DOR including the median will be characterized using the Kaplan-Meier method. 	Investigator Assessment 
 • Same as per primary analysis method based on Investigator assessment Internal computational assessment: 
 • Same as per primary analysis method based on ORCA assessment.
Time to Response	Safety Analysis Set: 
 • Based on Independent Review Committee • Non-missing sample size (n), mean, standard deviation, median, minimum, and maximum. 	Investigator Assessment 
 • Same as per primary analysis method based on Investigator assessment Internal computational assessment: 
 • Same as per primary analysis method based on ORCA assessment.
Progression Free survival (PFS)	Safety Analysis Set: 
 • Based on Independent Review Committee • The 90% and 95% CIs for PFS rate will be reported using the methods by Kalbfleisch and Prentice (1980) with log-log transformation. • The distribution of PFS, including median, will also be estimated using the Kaplan-Meier method. • The 90% and 95% CIs for the median and other percentiles of PFS will be constructed using the method of Klein and 	Investigator Assessment 
 • Same as per primary analysis method based on Investigator assessment Internal computational assessment: 
 • Same as per primary analysis method based on ORCA assessment. Per protocol population 
 • Same as per primary analysis method based on per protocol population Modified safety population

Endpoint	Primary Summary and Analysis Method (Specify Analysis Set if FAS is Not Used)	Sensitivity Analysis
	Moeschberger (1997) with log-log transformation.	
 • Same as per primary analysis method based on modified safety population.
Overall Survival	Same method described for PFS.	
Per protocol population
 
 • Same as per primary analysis method described for PFS based on per protocol population 
Modified safety population
 
 • Same as per primary analysis method described for PFS based on modified safety population.
Complete Response rate or better rate	Same methods as described for ORR.	
Investigator Assessment
 
 • Same as per primary analysis method described for ORR based on Investigator assessment 
Internal computational assessment:
 
 • Same as per primary analysis method described for ORR based on ORCA assessment. 
Per protocol population
 
 • Same as per primary analysis method described for ORR based on per protocol population 
Modified safety population
 
 • Same as per primary analysis method described for ORR based on modified safety population.

9.5.1 Analyses of Primary Efficacy Endpoint(s)/Estimand(s)

The primary analyses will be based on the safety analysis set, while the MRD sensitivity analyses will be performed on the MRD-evaluable analysis set.

Overall Response Rate (ORR)

It will be calculated along with the associated 90% and 95% exact binomial CIs that will be estimated using the Clopper-Pearson method. **The lower bound of the 90% exact binomial CI is evaluated whether it is larger than the reference ORR. If that happens, then the primary objective is met.**

9.5.2 Analyses of Secondary Efficacy Endpoint(s)

Key Secondary Efficacy Endpoint:

MRD[-]CR at sensitivity of 10^{-5} using NGS-based method in the bone marrow at 12 months \pm 4 weeks from start of treatment.

The rate will be calculated along with the associated 90% and 95% exact binomial CIs that will be estimated using the Clopper-Pearson method. **If the primary objective is met, then the lower bound of the 90% exact binomial CI is greater than the reference MRD[-]CR rate. If that happens, the key secondary objective is met.**

Secondary Efficacy Endpoint:

MRD[-] response at a sensitivity of 10^{-5} using NGS based method in the bone marrow at any time during therapy

It will be analyzed using the same method as described for the **key secondary** endpoint.

Sustained MRD[-]CR

It will be calculated along with the associated 90% and 95% exact binomial CIs that will be estimated using the Clopper-Pearson method.

Sustained MRD[-]CR at 24 months \pm 4 weeks

It will be calculated along with the associated 90% and 95% exact binomial CIs that will be estimated using the Clopper-Pearson method.

Duration of Response (DOR)

The distribution of DOR including the median will be characterized using the Kaplan-Meier method based on the subjects who achieve best overall response of sCR, CR, VGPR or PR.

Time to Response

Time to response will be summarized with the non-missing sample size (n), mean, standard deviation, median, minimum, and maximum for responders, ie, subjects who achieve best overall response of sCR, CR, VGPR, or PR.

Progression Free Survival (PFS)

The distribution of PFS, including median, will be estimated using the Kaplan-Meier method. PFS rate at selected time points (12 months and 24 months) will be reported. The 90% and 95% CIs for the median and other percentiles of PFS will be constructed using the method of Klein and Moeschberger (1997) with log-log transformation. The 90% and 95% CIs for PFS rates will be estimated using the methods by Kalbfleisch and Prentice (1980) with log-log transformation. **The subcategory of death with the primary reason of COVID-19 infection or COVID-19 pneumonia will be included in the PFS events.**

Overall Survival (OS)

OS will be analyzed using the same method as described for the PFS endpoints.

Complete Response or better rate (CRR)

The CR will be analyzed using the same methods as described for ORR.

9.5.3 Analyses of Exploratory Efficacy Endpoint(s)

Assess the depth of MRD

Percentage of the MRD[-] below the threshold of 10^{-4} , 10^{-5} and 10^{-6} by NGS-based method at time of suspected CR or better will be summarized.

PFS by depth of MRD response at: 10^{-4} , 10^{-5} and 10^{-6}

The correlation between MRD status and PFS will be explored in the MRD Evaluable Analysis Set. In the MRD Evaluable Analysis Set, subjects will be categorized into following subgroups: subjects who achieve MRD[-] any time during study and subjects who don't achieve MRD[-] any time during study, subjects who achieve MRD[-]CR any time during study and subjects who don't reach MRD[-]CR any time during study. Within each subgroup the distribution of PFS including the median and corresponding 95% CI will be summarized descriptively using the Kaplan-Meier method. Three different thresholds (10^{-4} , 10^{-5} and 10^{-6}) will be explored to define MRD status. The Cox proportional hazard model will also be fitted with MRD[-] status or MRD[-]CR status as

the time-dependent covariate to explore the correlation between MRD status and PFS. In addition, similar analysis may be done for MRD response at 12 months and 24 months landmarks. **When there is not a sufficient number of subjects in the subgroup, i.e., less than 10% of the MRD population, the analysis will not be conducted.**

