9.2.2.2 Bone Marrow Sample Evaluation Including FISH and MRD[-]CR Assessment

A baseline bone marrow aspirate sample will be collected at screening, or prior to dosing at cycle 1 day 1. A bone marrow sample obtained as standard of care may be used as the baseline sample if taken within 45 days prior to enrollment for FISH and MRD testing. The first sample obtained for baseline bone marrow aspirate will be for tumor specific sequence identification for MRD measurement by next-generation sequencing (NGS) at the central lab.

After screening, bone marrow aspirate will be obtained:

- at time of suspected CR or better. Depending on when this procedure occurs, an additional aliquot of bone marrow aspirate will be frozen and saved at the central lab for MRD testing to be performed at a later time.
- at time of MRD assessment. MRD will be conducted in subjects with suspected CR or better at 12 months (\pm 4 weeks) but may be performed as early as 8 months after start of treatment in subjects with suspected CR or better. Subjects with a MRD[-]CR response at the first time point should have the subsequent MRD assessment 12 months \pm 4 weeks after the earlier assessment, if subjects have not relapsed nor started new antimyeloma therapy prior to this subsequent MRD assessment.

If the bone marrow aspirate sample taken is found to be of insufficient quantity or quality for testing, the site may be contacted to request provision of a suitable archival bone marrow aspirate sample.

9.2.2.3 Bone Lesion Assessment (Skeletal Survey, Computed Tomography [CT], or Positron Emission Tomography/CT [PET/CT])

Skeletal survey will include lateral radiograph of the skull, anteroposterior and lateral views of the spine, and anteroposterior views of the pelvis, ribs, femora, and humeri. Low-dose whole body computed tomography or fluorodeoxyglucose-positron emission tomography/computed tomography (FDG-PET/CT) may be used in place of skeletal survey. Bone lesion assessment at screening (all subjects) may be done within 28 days prior to enrollment, if performed as a part of standard of care. It should be repeated if worsening clinical symptoms suggest PD or as clinically indicated. The same method of

assessment used at baseline will be used throughout the study. These imaging studies will be read locally.

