
Number of doses of pomalidomide administered

It is defined as the total number of non-zero doses of pomalidomide a subject received during the treatment period of the study

Number of doses of dexamethasone administered

It is defined as the total number of non-zero doses of dexamethasone a subject received during the treatment period of the study

Overall Response (OR)

OR is the best overall confirmed response of partial response (PR), very good partial response (VGPR), complete response (CR), or stringent complete response (sCR).

Overall Response Rate (ORR)

Overall Response Rate (ORR) is defined as the proportion of subjects that reach the overall response among all subjects who received at least 1 dose of the carfilzomib.

Overall Survival (OS)

OS is defined as time from start of treatment until death from any cause.

$OS = (\text{Death date or date of censoring if censored} - \text{start of any study treatment date} + 1) / 30.4$

Subjects still alive will be censored at the date last known to be alive. If the date last known to be alive is after the date that triggers the analysis (ie, the data cutoff date), the subject will be censored at the analysis trigger date.

Progression Free Survival (PFS)

PFS is defined as the time from the first dose date of any study treatment until the first documentation of disease progression or death due to any cause, whichever occurs first in the absence of subsequent anticancer therapy and if not > 70 days from the last non-NE, post-baseline disease assessment. PFS will be censored at the last non-NE, post-baseline disease assessment or the earlier of the following, where applicable: (a) the last non-NE, post-baseline disease assessment prior to subsequent anticancer therapy, or (b) the last non-NE, post-baseline assessment followed > 70 days later by disease progression or death; otherwise, at first dose date. Disease progression is based on the IMWG-URC [2016].

PFS time in months= [(PD or death date, whichever occurs first) or date of censoring if censored– start of treatment date + 1] / 30.4.

Table 5-1. Conventions for Censoring for PFS

Situation	Date of Progression or Censoring	Outcome
No PD or death, no new anticancer treatment	Last visit; otherwise, first dose date of any study treatment	Censored
No PD or death, new anticancer treatment	Last visit prior to new treatment; otherwise, first dose date of any study treatment	Censored

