6.3 MRD Evaluable Analysis Set

The MRD Evaluable Analysis Set includes all enrolled subjects with measurable MRD status at baseline and at least 1 measurable MRD status postbaseline (subjects who don't have measurable MRD status due to technical issues will be excluded), who received at least 1 dose of carfilzomib. The MRD sensitivity analysis will be based on MRD Evaluable Analysis Set.

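### The time-dependent Cox model of MRD status on PFS is fitted in subjects selected for a later MRD result, without delayed entry; when marrow dates differ, this pushes the hazard ratio up, against MRD negativity

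*SAP*

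**What the plan says.** - **Population.** SAP 9.5.3 opens the MRD-PFS analysis with: "The correlation between MRD status and PFS will be explored in the MRD Evaluable Analysis Set". It names no other population for the Cox model.
- **Model.** MRD[-] or MRD[-]CR status enters as "the time-dependent covariate to explore the correlation between MRD status and PFS". Nothing is said about when a subject enters the risk set.
- **Membership.** SAP 6.3 requires a measurable baseline status and "at least 1 measurable MRD status postbaseline".
- **Time origin.** SAP section 5 (Progression Free Survival): "PFS is defined as the time from the first dose date of any study treatment until the first documentation of disease progression or death".
- **Marrow timing.** Protocol 9.2.2.2 schedules MRD at 12 months ± 4 weeks in subjects with suspected CR or better, but it "may be performed as early as 8 months after start of treatment in subjects with suspected CR or better". The same section takes a marrow whenever CR is suspected and, depending on timing, stores an aliquot for later MRD testing.
- **Alternatives in the plan.** SAP 9.5.3 also gives Kaplan-Meier summaries by MRD status ever or never reached. Landmark analyses at 12 and 24 months are optional. The section ends with a rule that drops the analysis when a subgroup is below 10% of the MRD population.

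**The concern.** A time-dependent covariate removes guarantee-time bias only if membership of the analysis set does not depend on the future. Here it does. A subject must stay progression-free long enough to be sampled at suspected CR or better, so anyone who progresses or dies before the first marrow never enters the set. Those are the events that belong to the not-negative state.

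The members who remain are at risk from first dose, coded as not negative until a negative result, and cannot fail before their marrow. The hazard of the not-negative state is then understated and the hazard ratio for MRD negativity is too high.

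At stake is a stated exploratory objective in both documents, the correlation between MRD status and PFS. Protocol Amendment 4 moved MRD[-]CR out of the primary position because its relationship to standard endpoints was not established, so this is the trial's own evidence on that relationship. Readers tend to trust a time-dependent model as the version free of timing bias.

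**Working it through.** Neither document gives a hazard ratio, event count or power for this analysis, so there is no planned figure to reproduce.

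**Step 1: the bias at one event time.** Among set members at risk at time t, let n1 be MRD-negative, n0 sampled and not negative, and w still awaiting their marrow. Let the hazard be h in the n0 group and θh in the n1 group. It is 0 in the w group, by selection. The model pools n0 and w as not negative, so the pooled hazard is h × n0/(n0 + w) and the apparent ratio is

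θ × (n0 + w)/n0 = θ × (1 + w/n0).

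This is never below θ, and it equals θ only when w = 0. The partial likelihood uses only event times, so waiting time before any member has failed contributes nothing. Harm arises when one member progresses while another is still waiting.

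*Illustration.* Take marrows uniform over months 8-13, half of the sampled subjects negative, and ignore members who have already failed. At month 10.5 the waiting share is (13 − 10.5)/(13 − 8) = 0.5 and the n0 share is 0.5 × 0.5 = 0.25. The apparent ratio is θ × (1 + 0.5/0.25) = 3θ. After month 13, w = 0 and the ratio is θ. Most events come after month 13, so the overall estimate lies much nearer θ than 3θ.

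**Step 2: the overall hazard ratio by simulation.** About 300,000 subjects per scenario.

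- From the documents: PFS origin at first dose; set membership as in SAP 6.3; marrow windows built from Protocol 9.2.2.2 and the month 8 to 12-plus-4-weeks window in SAP section 5.
- Assumed: half of sampled subjects MRD-negative; exponential time from marrow to event, median 9-24 months; censoring uniform over months 12-34; suspected-CR marrows starting at month 4 in the widest window; a lag of 0 or 1 month between marrow and first possible event.

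| First marrow | Lag | Fitted HR when the true HR is 1.00 |
|---|---|---|
| All on one date | 0 | 1.00 |
| Months 11-13 | 0 | 1.08-1.10 |
| Months 11-13 | 1 month | 1.01-1.02 |
| Months 8-13 | 0 | 1.17-1.25 |
| Months 8-13 | 1 month | 1.09-1.13 |
| Months 4-13 | 0 | 1.31-1.45 |
| Months 4-13 | 1 month | 1.23-1.30 |

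With a true HR of 0.50, the fitted value is 0.58-0.60 for months 8-13 without a lag, 0.54-0.55 with a 1-month lag, and 0.63-0.67 for months 4-13 without a lag. Simulation error is about 0.01-0.02.

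**Step 3: a second model.** This used exponential PFS from first dose with median 7.2, 12 or 18 months (the span of Protocol Table 5-1), 30% or 60% MRD-negative, and censoring at 36 months. With no true association the fitted HR was 1.00-1.01 with all marrows at month 12, 1.02-1.10 for months 11-13, 1.08-1.25 for months 8-13, and 1.17-1.54 for months 2-13. Wherever marrow dates differed, the shift was upward.

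**Step 4: with delayed entry.** When subjects enter at the first marrow, the fitted HR is 0.99-1.02 for a true 1.00 and 0.49-0.51 for a true 0.50, across both models.

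**The case against.** **Timing.** The scheduled marrow is at 12 months ± 4 weeks, and month 8 is only a permitted early option. Disease is assessed every 28 ± 7 days, so progression is unlikely to be documented on the day of a suspected-CR marrow. With marrows at months 11-13 and a 1-month lag, the bias almost vanishes (about 1.01). This stands. A reader might infer that the model as specified will show harm from MRD negativity when none exists; the documents do not support that as an unconditional statement. They do allow an 8-13 month spread, and marrows at suspected CR can widen it.

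**Precision.** If 10-20 subjects are evaluable (an assumption), about 5-10 events would be expected and the standard error of the log HR would be about 0.7-1.1. The 95% limits are then the estimate divided and multiplied by roughly exp(1.96 × 0.7) = 3.9 to exp(1.96 × 1.1) = 8.6. The bias on the log scale is only about ln 1.09 = 0.09 to ln 1.25 = 0.22. Random error will dominate. This limits the consequence, but it does not justify leaving in a directional error that is free to remove.

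**Place in the plan.** A reader might also infer that this Cox model is the only firmly planned analysis of the objective that avoids guarantee-time bias. That goes too far: the 10% rule can be read as cancelling it too, and landmark versions are named. They are optional, however, so the Cox model is still more firmly planned than they are.

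**The alternative repair.** Fitting the model in the full Safety Analysis Set changes the comparator to all treated subjects not yet negative, including non-responders and early progressors. This stands, and the two repairs are not interchangeable.

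**Conclusion.** The point holds as a conditional bias of known direction. The model is fitted in a set defined by a future MRD result, with time from first dose and no delayed entry. Whenever first marrow dates differ and events occur while some members still wait, the hazard ratio moves up, against MRD negativity.

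With no true association, the shift runs from none (all marrows on one date) through about 1.01-1.10 (months 11-13) and about 1.09-1.25 (months 8-13) to about 1.2-1.45 if suspected-CR marrows from month 4 count. These sizes rest on the assumed MRD-negative share, PFS after the marrow, censoring, marrow spread and lag. They are not properties of the trial's data.

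The consequence is confined to the interpretation of one exploratory association, in a small subset of 52 treated subjects. ORR, the 12-month MRD[-]CR rate and their decision rules are unaffected.

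**What to change.** In SAP 9.5.3, add one sentence: in the Cox model, each subject enters the risk set at the collection date of the first post-baseline MRD sample, with MRD status updated over time from then. Use the collection date rather than the test date, because stored aliquots may be tested later.

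If a model in the full Safety Analysis Set is also wanted, with subjects counted as not negative until a negative result, label it as a supplementary analysis of a different question.

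The cost is one sentence and an entry-time option in the existing Cox code. No new data are needed. Delayed entry keeps the population chosen in the SAP and discards only risk time in which no set member could have had an event.
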